# 6.7. Discontinuation from the Study

Subjects may voluntarily discontinue from the study for any reason at any time.

#### 6.7.1. Withdrawal of Consent

Subjects may voluntarily withdraw consent to participate in the study for any reason at any time.

Withdrawal of consent occurs only when a subject does not want to participate in the study anymore and does not want any further visits or assessments and does not want any further study related contact.

If a subject withdraws consent, the Investigator must make every effort to determine the primary reason for this decision and record this information. Further attempts to contact the subject are not allowed unless safety findings require communicating or follow-up. The Sponsor may retain and continue to use any data collected before consent was withdrawn.

#### 6.7.2. Early Study Termination

The study can be terminated at any time for any reason by the Sponsor. Should this be necessary, subjects should be seen as soon as possible and treated as a prematurely withdrawn subject. The Investigator may be informed of additional procedures to be followed in order to ensure that adequate consideration is given to the protection of the subject's interests.

The Investigator will be responsible for informing IRBs of the early termination of the study.

# 7. ADVERSE EVENT AND SERIOUS ADVERSE EVENT DOCUMENTATION

PLEASE SEE THE STUDY OPERATIONS MANUAL FOR DETAILED INSTRUCTIONS ON REPORTING OF SAEs, INCLUDING EMERGENCY CONTACT INFORMATION (eg, FAX, EMAIL OR TELEPHONE CONTACT NUMBERS)

## 7.1. Evaluation of Safety

Timely, accurate, and complete reporting and analysis of safety information from clinical studies are crucial for the protection of subjects and is mandated by Regulatory Agencies worldwide. All clinical studies sponsored by RADIUS will be conducted in accordance with Standard Operating Procedures that have been established to conform to regulatory requirements worldwide to ensure appropriate reporting of safety information.

All AEs are collected from the time of signing the informed consent until 7 days after last dose of investigational product. At any time after 7 days from the last dose of study treatment, the investigator may report any SAE that he/she believes is possibly related to study treatment. Where possible, a diagnosis rather than a list of symptoms should be recorded. All AEs should be captured on the appropriate AE pages in the eCRF and in source documents. The Investigator will assess the relationship of all AEs to the study drug.

#### 7.1.1. Adverse Event

An AE is any untoward medical occurrence in a clinical investigation subject administered a pharmaceutical product and that does not necessarily have a causal relationship with this treatment. An AE can therefore be any unfavorable and unintended sign (including an abnormal laboratory finding), symptom, or disease temporally associated with the use of a medicinal (investigational) product, whether or not related to the medicinal (investigational) product

AEs could include:

- Worsening (change in nature, severity, or frequency) of conditions present at the onset of the study
- Intercurrent illnesses
- Drug interactions
- Events related to or possibly related to concomitant medications
- Clinically significant abnormal laboratory values (this includes significant shifts from Baseline within the range of normal that the Investigator considers to be clinically important)
- Clinically significant abnormalities in physical examination, vital signs, and weight

An abnormal laboratory value will not be assessed as an AE unless it requires a therapeutic intervention or is considered by the Investigator to be clinically significant.

When possible, a clinical diagnosis for the study assessment should be provided rather than the abnormal test result alone (eg, urinary tract infection, anemia). In the absence of a diagnosis, the

abnormal study assessment itself should be listed as the AE (eg, bacteria in urine or decreased hemoglobin).

Determination of clinical significance must be made by the Investigator.

All skin reactions at the application site reported by the subject and investigator, expected or unexpected, and regardless of severity will be reported as AEs and should include reference to the application site. Events of ulcer, eschars, and non-healing wounds at the application site will be evaluated as an adverse event of special interest (Skin AESI). Skin AEs that occur at other locations of the body should be reported as AEs as appropriate but are not to be recorded/entered using phrases such as 'at the application site', 'involving the application site', etc., to ensure the phrase 'application site' is used exclusively for the sites of study drug administration.

#### 7.1.2. Serious Adverse Event (SAE)

An SAE is any AE that results in any of the following:

- Death
- Life-threatening: The term "life-threatening" in the definition of "serious" refers to an event/reaction in which the subject was at risk of death at the time of the event/reaction; it does not refer to an event/reaction which hypothetically might have caused death if it were more severe.
- Hospitalization or prolongation of existing hospitalization.
- Persistent or significant disability/incapacity (ie, substantial disruption of the ability to conduct normal life function).
- Congenital anomaly/birth defect.
- Important medical events that may not result in death, are life-threatening, or require hospitalization may be considered serious when, based upon appropriate medical judgment, they may jeopardize the subject and may require medical or surgical intervention to prevent one of the outcomes listed in this definition. Examples of such medical events include allergic bronchospasm requiring intensive treatment in an emergency room or at home, blood dyscrasias or convulsions that do not result in subject hospitalization, or the development of drug dependency or drug abuse.

All AEs of osteosarcoma will be reported as SAEs.

All treatment related AEs/SAEs noted on the follow-up visit must be followed until resolution (subject has returned to baseline status of health) or until stabilization (the Investigator does not expect any further improvement or worsening of the reported event), or until the subject is lost to follow-up.

#### 7.1.3. Recording an Adverse Event

All AEs/SAEs spontaneously reported by the subject and/or in response to an open question from study personnel or revealed by observation, physical examination, or other diagnostic procedures must be recorded in the source document and entered into the electronic database.

Planned hospital admissions or surgical procedures for an illness or disease that existed before the subject was enrolled in the study are not to be considered AEs unless they occur at a time

other than the planned date or the pre-existing illness or disease worsens after enrollment into the study.

For both serious and non-serious adverse events, the Investigator must determine the intensity of the event and the relationship of the event to study drug administration. Intensity for each AE will be defined according to the following criteria:

Intensity	Definition
Mild	Awareness of sign or symptom, but easily tolerated.
Moderate	Discomfort enough to cause interference with normal daily activities.
Severe	Inability to perform normal daily activities.

If the intensity of an adverse event changes within a day, the maximum intensity should be recorded. If the intensity changes over a longer period of time, the changes should be recorded as separate events (having separate onset and stop dates for each intensity).

Relationship to study drug or device, defined as study drug administration will be determined by the Investigator according to the following criteria:

Relationship	Definition
None	No relationship between the event and the administration of study drug. The event is related to other etiologies, such as concomitant medications or subject's clinical state.
Unlikely	The current state of knowledge indicates that a relationship to study drug administration is unlikely or the temporal relationship is such that study drug administration would not have had any reasonable association with the observed event.
Possible	A reaction that follows a plausible temporal sequence from administration of the study drug and follows a known response pattern to the suspected study drug. The reaction might have been produced by the subject's clinical state or other modes of therapy administered to the subject.

Relationship Do	efinition
------------------------	-----------

Probable A reaction that follows a plausible temporal

sequence from administration of the study drug and follows a known response pattern to the suspected study drug. The reaction cannot be reasonably explained by the known characteristics of the subject's clinical state or other modes of therapy administered to the subject.

For the purpose of safety analyses, all AEs that are classified with a relationship to study medication administration of possible or probable will be considered treatment-related events. The AE will be determined to be device-related if it is identified to have had a probable or possible causal relationship to the investigational device.

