## 7.1.6. Follow-up of Adverse Events

All treatment-related AEs will be followed with appropriate medical management until resolved or stabilized, or the subject is lost to follow-up. UADEs will be followed until their medical outcome is determined, with periodic written reports about the status provided to the study Sponsor.

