#### 7.1.8. Regulatory Agency, Institutional Review Board, and Site Reporting

The sponsor and/or the clinical contract research organization are responsible for notifying the relevant regulatory authorities/ IRBs of related, unexpected SAEs.

The investigator is responsible for notifying the sponsor, CRO, and local IRB, or the relevant local regulatory authority of all SAEs that occur at his or her site as required.

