4.8.1 Adverse Events

Analyses of AEs will be performed for those events that are considered to be treatment-emergent adverse events (TEAEs). A TEAE is defined as any AE that was absent (i.e., had not occurred) prior to the start of study drug and which occurs on or after the date of the first dose of study drug and within 30 days of the last dose of study drug, or any AE that started during the study period(s) prior to the start of study drug and worsened in severity after the start of study drug within 30 days of the last dose of study drug.

In any tabulation of adverse events, a subject contributes only once to the count for a given SOC or PT. For summaries by severity, a subject with multiple occurrences of an AE will be represented under the most severe occurrence. For summaries by relationship to study drug, a

subject with multiple occurrences of an AE will be represented under the most related occurrence.

The number (%) of subjects with TEAEs will be summarized by SOC and PT. This analysis will also be performed for the following types of AEs: most common ($\geq 5\%$) TEAEs, severe TEAEs, serious TEAEs (SAEs), TEAEs leading to study withdrawal, drug-related TEAEs (with probable or possible relationship to study drug), and AEs that are not treatment-emergent.

The number (%) of subjects with TEAEs by SOC and PT will also be tabulated by maximum severity (mild, moderate, or severe). Subjects with multiple occurrences of a single AE will be counted using the most severe AE. A similar tabulation will be presented by relationship (related or not related) to study drug.

TEAEs associated with the below AEs of special interest (AESI) will be summarized:

- Skin AESI
- Hypersensitivity AESI

Subject listings will be provided for all AEs by SOC and PT. Listings will also be produced for AEs with outcome of deaths, severe AEs, SAEs, AEs leading to discontinuation of study drug withdrawal, Skin AESI, Hypersensitivity AESI and unanticipated adverse device effects (UADEs).

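### Both related causality categories require a known response pattern, so a novel, plausibly timed reaction has no clear category and can be under-classified as not related

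*Protocol*

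**What the plan says.** Protocol 7.1.3 gives the investigator four relationship ratings.

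- **None**: there is no relationship, and "The event is related to other etiologies".
- **Unlikely**: "The current state of knowledge indicates that a relationship to study drug administration is unlikely", or the timing rules out a reasonable association.
- **Possible**: the reaction "follows a plausible temporal sequence from administration of the study drug and follows a known response pattern to the suspected study drug"; the subject's condition or another therapy might also have produced it.
- **Probable**: the reaction again follows a plausible temporal "sequence from administration of the study drug and follows a known response pattern to the suspected study drug", and the subject's condition or other therapy cannot reasonably explain it.

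The same section then groups the ratings: AEs with a "relationship to study medication administration of possible or probable will be considered treatment-related events". SAP 4.8.1 uses the same grouping for "drug-related TEAEs (with probable or possible relationship to study drug"), as does Protocol 8.4.4.

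The label is used again elsewhere. Protocol 7.1.6 says "All treatment-related AEs will be followed with appropriate medical management until resolved or stabilized" or the subject is lost to follow-up. Protocol 7.1.4 makes reporting of SAEs after study completion depend on the investigator considering them related. Protocol 7.1.8 makes the sponsor and/or CRO "responsible for notifying the relevant regulatory authorities/ IRBs of related, unexpected SAEs". The protocol does not define the term unexpected; 7.1.4 says only that the reference safety information is in the IB.

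**The concern.** A known response pattern is reasonable supporting evidence for causality. Here it is a necessary condition, and it applies to both ratings that count as related, so no lower related rating catches an event without precedent.

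That matters in this study because knowledge of repeated use of the product is still being built. Protocol 1.2 describes earlier use of this same product as a single dose applied by a trained healthcare professional. Section 1.1.2.2.2 says the earlier sMTS studies used a different (PBS) formulation, and 1.1.2.1 says dermal sensitization and toxicology studies with the sMTS are ongoing or planned. This study has subjects apply the product themselves every day for 29 days. A reaction not seen before is one of the things its safety data should be able to show as related, and any error the wording causes runs toward not related.

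**Working it through.** No arithmetic underlies the main point. The check is to take one test event and hold it against each definition. The event starts at a plausible time after dosing, has no other explanation, and has no precedent with the drug.

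| Rating | What 7.1.3 requires | Does the test event meet it? |
|---|---|---|
| None | No relationship; another cause accounts for the event | No: there is no other cause |
| Unlikely | Current knowledge points against a relationship, or the timing does not fit | Timing fits; met only if having no knowledge is read as knowledge against |
| Possible | Plausible timing **and** known pattern | No: no known pattern |
| Probable | Plausible timing **and** known pattern **and** no other reasonable explanation | No: no known pattern, although the other two conditions are met |

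The event fits no rating cleanly, and on the text as written it cannot be rated related.

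Next, what depends on the label and what does not:

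| Depends on the rating | Does not depend on it |
|---|---|
| Drug-related TEAE tables (Protocol 8.4.4, SAP 4.8.1) | All-TEAE, severe, serious and AESI summaries (same sections) |
| Follow-up to resolution or stabilization (7.1.6) | Application-site reactions: all recorded as AEs (7.1.1); those ongoing on Day 29 assessed until resolved or stabilized (6.6.2.1) |
| Required reporting of SAEs after study completion (7.1.4) | All SAEs from consent to 7 days after the last dose, reported within 24 hours (7.1.4) |
| Notification of related, unexpected SAEs (7.1.8) | UADEs: own definition with no known-pattern test (7.1.3.1), reportable to 30 days after the last dose (7.1.5) |

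Size of one misrating in a drug-related table:

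- Planned number treated: about 22 (Protocol synopsis).
- Counting rule: a subject counts once per SOC or preferred term (SAP 4.8.1).
- If the subject is not already counted in that row, the shift is 1/22 = 0.045, or 4.5 percentage points. If the subject is already counted there, the shift is 0.

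So 4.5 points is the maximum per row for one misrated subject. The documents give no basis for estimating how many such events would occur.

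**The case against.** The strongest case on the other side has four parts.

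**Most safety detection does not use the label.** This stands, and it limits the reach of the point. The right-hand column above covers in-study SAEs, application-site reactions and UADEs. In addition, Protocol 6.5.1 has significant or unexplained laboratory abnormalities followed until normal or explained. What remains exposed is the relatedness tabulation of any novel event, follow-up of novel events outside those groups, and SAEs arising later.

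**The text does not direct a not-related rating.** Unlikely calls for knowledge that points against a relationship, and absence of precedent is not that. An investigator may also rate by judgment: 7.1 and 7.1.4 refer, for later SAEs, to what the investigator believes or considers, without citing the table. This stands in part. The defect is a gap that can produce under-classification, not a rule that forces it, and how literally the definitions would be applied is unknown.

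**A stronger reading is not supported.** A reader might infer that, since a related event must follow a known pattern, no SAE can be both related and unexpected, so the 7.1.8 notification could never be triggered. That equates a known response pattern with expectedness, which the documents never do. A pattern may be known from pharmacology or animal data without being listed in the reference safety information, or may be listed at lower severity. Protocol 1.1.2.2.1 shows how the sources can differ: osteosarcoma was dose-dependent in rats, with no cases in the abaloparatide-SC clinical program. The IB is not available here, so the overlap cannot be measured.

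**Simply deleting the condition would overshoot.** With daily dosing, most on-treatment events have plausible timing. If Possible needed only that, with another cause also conceivable, it could take in most TEAEs and blunt the related/not-related split. This stands and shapes the fix.

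**Conclusion.** The point holds in a limited form. As written, a first-of-its-kind reaction with plausible timing and no other explanation meets neither related rating and has no clear home in the other two, so the scale can under-classify novel related events. The effect falls on the drug-related TEAE tables, on follow-up of novel AEs that are neither application-site reactions nor UADEs, on reporting of SAEs after study completion, and on part of the 7.1.8 notification. That last category is narrowed but not shown to be empty.

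The conclusion assumes that the definitions are applied as worded and that no other instruction to investigators softens them. The analyses affected are descriptive, so no formal test or sample-size statement changes.

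**What to change.** Amend Protocol 7.1.3 as follows.

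- **Probable**: require plausible timing and no reasonable explanation by the subject's clinical state or other therapy. Keep a known response pattern as supporting evidence, not a requirement.
- **Possible**: keep plausible timing, and replace the mandatory known pattern with an alternative, for example: *follows a known response pattern, or there is otherwise a reasonable possibility that the study drug or device caused the event*. This closes the gap without making timing alone sufficient.
- **Expectedness**: state that it is judged separately from causality, against the reference safety information in the IB.

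Align the eCRF completion guide with the new text. SAP 4.8.1 needs no change, because it refers to the ratings by name.

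The cost is a protocol wording change and an update to the guide. The downside is that some more events will be classed as related; the documents do not allow an estimate of how many.

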## 7.1.3.1. Serious and Unanticipated Adverse Device Effects for Abaloparatide-sMTS

An adverse device effect is defined as any adverse event that may or may not be related to the investigational abaloparatide-sMTS device and should be reported as an AE (Section 7.1.1), and includes AEs resulting from insufficient or inadequate instructions for use, deployment, implantation, installation, operation, malfunction, use error or from intentional misuse of the investigational medical device.

An unanticipated adverse device effect (UADE) is defined as any SAE on health or safety or any life-threatening problem or death caused by, or associated with, the abaloparatide-sMTS device, or any other unanticipated serious problem associated with a device that relates to the rights, safety, or welfare of subjects.

The Investigator and the Sponsor will immediately conduct an evaluation of any UADE occurring with abaloparatide-sMTS. The results of the evaluation will be reported to the IRB within 10 days of the Investigator and/or the Sponsor becoming aware of the event. If it is determined by the Investigator and the Sponsor to present an unreasonable risk to study participants, all investigations or parts of the investigation presenting that risk will be terminated as soon as possible. Termination will occur not later than 5 working days after the Investigator and the Sponsor makes this determination, and not later than 15 working days after first receiving notice of the event. The Investigator and the Sponsor will not resume an investigation terminated under these conditions without an additional IRB approval.

#### 7.1.4. Serious Adverse Event Reporting

Any SAEs that occur during the study from the time the subject signs the ICF until 7 days after the last dose of study medication must be reported within 24 hours of first awareness of the event by completing and faxing the SAE Form and entering data in the clinical trial eCRF. In addition, all SAEs including all deaths which occur up to and including 7 days after administration of the last dose of study drug, must be reported to the Medical Monitor within 1 working day. SAE forms will be provided to the clinical study site. The reference safety information for this study is included in the IB, which will be provided under separate cover to all investigators.

Any SAEs that occur at any time after completion of the study, which the Investigator considers to be related to study drug, must be reported to the Sponsor or its designee.

The Investigator must submit the SAE to the IRB in accordance with 21 CFR parts 56 and 312 as well as with applicable local regulations. Documentation of these submissions must be retained in the site study file.

## 7.1.5. Device Reporting

Abaloparatide-sMTS is a drug-device combination product. In order to fulfil regulatory reporting obligations worldwide the investigator is responsible for the detection and documentation of events meeting the definition of UADEs that occur with abaloparatide-sMTS (Section 7.1.3.1).

Any UADEs that occur during the study with abaloparatide-sMTS from the time the participant signs the ICF until 30 days after the last dose of study medication must be reported within 24 hours of first awareness that the event meets the definition of a reportable incident by entering data in the clinical trial eCRF. Treatment-related UADEs will be followed until resolution or stabilization, the condition is otherwise explained, or until the subject is lost to follow-up.

The investigator will comply with the applicable local regulatory requirements relating to the reporting to the IRB.

